### Possible Discomforts and Risks

The physiological (and perceptual) effects of *intermittent hypoxia* in humans are well studied at the degree and duration of hypoxia as proposed here, and appear safe and well-tolerated (7, 33). Similar AIH protocols have been shown to improve ventilation (72, 73), enhance cerebral blood flow (26), and increase muscle sympathetic nerve activity. More severe hypoxia (3-6% O2) and recurrent (>>15 episodes per day) have been associated over time with hypertension, increased systemic inflammation and neurocognitive deficits, as seen clinically in obstructive sleep apnea (8, 74, 75). On the other hand, intermittent hypoxia protocols consisting of less severe (>9% O2) and recurrent (<15 episodes/day) are associated with the opposite outcome, including reduced blood pressure, anti-inflammatory effects and neurocognitive enhancement (8, 74, 75). The hypoxia dose and duration have been carefully selected to optimize impact while minimizing known risks. We will monitor subjects continuously to detect adverse events, if any.

While this AIH protocol is well-tolerated and appears safe in most individuals, some patients may report transient light-headedness, dizziness, or reduced vision. Some patients also report an increase in respiratory sensation (mild to moderate shortness of breath), or rarely notice an increase in breathing (tidal volume) during the hypoxic periods. During and after the AIH protocol, we continuously monitor heart rate, respiratory rate, end tidal  $CO_2$  (ETCO2) and oxygen saturation (SpO2) as well as the rating of dyspnea. The FiO2 will be closely titrated to maintain SpO2 >78% during hypoxic episodes. While excessive HR and BP responses have not been reported, AIH will be stopped in the unlikely event the heart rate increases or decreases >30% from the resting value, and/or systolic blood pressure changes more than 30% from the resting value. Subjects will be informed that they can request to stop the study at any time. If SpO2 falls below 75%, the AIH intervention will be terminated and supplemental O2 provided.

Additionally, the mask interface for administering AIH and measuring breathing can feel warm, moist, and/or confining to some individuals. To offset discomfort, the mask will be removed during rest periods and between post-AIH measurements. We prefer to use a mask interface, since subjects are able to easily communicate while using a mask and it can accommodate patients with bulbar/oral weakness. However, if subjects cannot tolerate the mask, a mouthpiece and nose clip can be offered as an alternative.

Neurologic effects of low- to moderate-dose caffeine (3-6 mg/kg) include increases in alertness, mood, reaction time, and motor function (limb and possibly respiratory muscle strength, gait). (76-79). Higher doses of caffeine elicit concurrent A1 receptor competitive inhibition, which may increase heart rate and/or blood pressure. However, both population studies and controlled studies in heart failure indicate caffeine has either a neutral or protective effect on cardiovascular risk (80, 81) as well as arrhythmias (82), in acute doses up to 500 mg (83). Caffeine may promote feelings of anxiety or fear in some individuals. Caffeine-induced anxiety has been linked to known polymorphisms of the ADORA2A gene and is associated to an aversion of chronic caffeine consumption (84). Caffeine is also a weak, non-specific phosphodiesterase inhibitor. While phosphodiesterase

inhibition occurs only at high doses (>9 mg/kg) that exceed typical human consumption(45, 85), some individuals report stomach pain or queasiness after consuming caffeine.

To minimize possible side effects of caffeine, we will exclude subjects with known sensitivity to caffeine. This study will use a standard dose of 3 mg/kg, which is considered by FDA and EFSA (European Food Safety Authority) (86) to be a safe and well-tolerated quantity in most individuals. Additionally, caffeine is generally recognized as safe (GRAS) by FDA's regulations solely in cola-type beverages up to 0.02% (200 ppm). 21 C.F.R. § 182.1180.

The caffeine capsules will be compounded by Westlab Pharmacy, a PCAB Accredited® compounding pharmacy located approximately 2 miles from the University of Florida's campus. Capsules will contain caffeine powder and filler (cellulose gum) in order to help in the breakdown and absorption of the caffeine. Westlab Pharmacy will compound individual capsules at a dose corresponding to 3 mg caffeine per kg body weight. To meet the minimum compounding requirements of the external pharmacy, we will order 3-5 capsules corresponding to several pre-determined body weights (e.g. 5, 10, 25, 50, 60, 70, 80, 90, and 100 kg). Westlab Pharmacy will then provide subjects with the minimum number of capsules needed to approximate (but not exceed) a 3 mg/kg dose. Each subject will orally ingest the caffeine capsules with water.

Respiratory strength testing procedures increase voluntary respiratory drive of subjects, which in some patients can result in a briefly elevated heart and/or respiratory rate, and decreased SpO2, feelings of shortness of breath and exertion. Some individuals find the transient exertion caused by breathing tests to be uncomfortable or anxiety-provoking (87). These effects occur infrequently and resolve upon removal of the respiratory stimulus. Nevertheless, we will monitor vital signs during the respiratory tests and be certain that patients understand they can rest as long as they like between test bouts or stop any test at any time.

The surface EMG electrodes are secured to subjects with a double-sided adhesive tape, which can cause skin redness or irritation in some individuals with adhesive sensitivities. Subjects will be asked about any known skin sensitivities, and if present a hypo-allergenic tape will be used.

The sensors attached during the ECG and overnight sleep monitoring may also be uncomfortable and cause mild skin irritation in some individuals sensitive to adhesive tape. The study team will attach the ECG stickers. A hypo-allergenic tape will be used instead for these individuals.

Patients with ALS will be recruited from the UF ALS clinic, which encompasses a large catchment area. The study risks of *travel* for patients with neuromuscular disease include fatigue, muscle and joint pain, and difficulty with pressure relief and toileting regimens. In addition, test performance may be diminished by fatigue. Up to \$200 reimbursement has been budgeted for the cost of overnight lodging for patients.

For testing of *caffeine metabolism genes*, risks are extremely small but include the risk of exposing a subject's genetic information. To offset these risks, we will de-identify the

samples, and focus upon specific single nucleotide polymorphisms (SNP) in 3 genes that have essential known functions relating to caffeine metabolism (CYP1A2 and ADORA2A) and synaptic plasticity (BDNF). Caffeine metabolism genes and salivary caffeine levels will be analyzed at UF's ICBR, to minimize exposure of a subject's genetic information.

Safety oversight will occur internally through the UF IRB-01 as well as through a data safety monitoring board (DSMB). The DSMB will be convened before enrollment of the first patient, after completion of the first three patients, and at least annually thereafter. The DSMB will include three members - 1 expert in intermittent hypoxia, one in sleep/pulmonary medicine, and one in rehabilitation. At least 1 member will be external, since a wealth of external expertise in intermittent hypoxia expertise is available and this issue is of great interest to the scientific community. Notes will be taken and available for the IRB at continuing review.

Testing and enrollment of subjects will be paused and the DSMB will be convened, if any of the following events occur: (1) a clinically significant respiratory event determined by the PI to be related to study procedures, (2) a clinically significant cardiovascular event determined by the PI to be related to study procedures, (3) a serious adverse event as defined by IRB-01. Any subsequent study activities would only be resumed when cleared or modified by the IRB-01 and DSMB.

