The dose of intermittent hypoxia is critical in determining the direction and extent of plasticity, and the potential for adverse events (8). For example, high doses of intermittent hypoxia simulating obstructive sleep apnea [80 or more episodes per day/night; severe hypoxemia within each episode] elicit pathology, including systemic hypertension, neuroinflammation, and cognitive impairment (23, 24). On the other hand, respiratory motor plasticity is undermined by severe intermittent hypoxia protocols due to neuroinflammation (25). **In striking contrast**, repeated, low dose AIH [<15 episodes per day; modest hypoxemia per episode] elicits neuroplasticity without detectable pathology (26-31). To the contrary, repetitive low dose AIH exerts beneficial effects in multiple organ systems by independent research groups (for review see: (8)).

Here, we propose to study mechanisms of respiratory plasticity associated with a single presentation of mild AIH. AIH is simple to apply and well tolerated by most individuals. In eight studies on humans with chronic spinal cord injury published to date, an AIH protocol similar to that proposed here has not been associated with any adverse events (5, 7, 31-35). Several other completed, but not yet published studies from multiple laboratories increase our collective experience with (and confidence in) this protocol (Christensen et al., submitted; Sandhu et al., in preparation; Ahmed et al., in preparation). All available evidence is consistent with the conclusion that AIH protocols similar to that proposed here are safe in humans, although we do not yet have experience with ALS

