## Eligibility Criteria.

Subjects will be eligible to participate if they have a clinical diagnosis of ALS or are a healthy adult; are between 21 and 75 years of age; and have a baseline FVC >60% predicted for age, sex and height. Baseline FVC is routinely performed at every clinic for ALS patients. The AIH study team (PI or coordinator) will email a PFT report request to the clinic respiratory therapist, in advance of clinic. On the day of clinic, the respiratory therapist will upload the requested PFT reports directly into EPIC. After clinic, the AIH study coordinator will locate the PFT report in EPIC and save it to the electronic study binder. If the PFT report indicates the FVC is within study criteria, the subject can be contacted for an appointment. If the FVC falls below study eligibility, the patient will not be scheduled for a screening visit.

Patients will be classified into two groups: 1) uses no form of external respiratory support (IND); and 2) and uses non-invasive external respiratory support while sleeping for at least 2 nights per week to assist night time breathing or treat sleep apnea (NIV). Since 4-6 subjects in each group may fail to meet all eligibility criteria or attend the second testing session, we request to enroll up to 18 patients with ALS, with the goal of completing all study procedures in 12 patients. In addition, we request enrollment of up to 30 healthy controls to complete all study procedures in 20 (up to 20 healthy controls may be needed as a reference set for the EMG data analysis described on *page 10*). The healthy controls will be recruited via listings for this study on CT.gov and the StudyConnect website.

Patient and control participants are ineligible if they: are pregnant, have diagnosed cardiovascular disease, have a BMI >35 kg/m^2, currently take selective serotonin reuptake inhibitors (SSRI), have a history of seizures, have a history of hospitalization for sepsis, had a respiratory infection or took antibiotic medications within the past 4 weeks, use external respiratory support during any waking hours, participate in a pharmaceutical trial to treat ALS, or have any other medical condition the PI ([name]) or medical director ([name]) identify would make it unsuitable to participate.

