Additionally, subjects will be ineligible to participate in Aim 3 (caffeine+AIH) if they: report negative side effects to caffeine consumption (e.g. anxiety, dizziness); have a diagnosis of diabetes (due to effect of caffeine on glucose metabolism (55) or hepatic cirrhosis (impaired metabolism of caffeine (56), or take antiarrhythmic or bronchodilator medications (57).

The sample size is consistent with the time and budget required to acquire strong pilot data for an NIH R01 grant, which is the major goal of this project.

Eligible subjects who agree to participate and sign the informed consent form approved by UF will undergo further screening procedures prior to beginning study procedures. Screening will include a detailed medical and pharmacological history, caffeine consumption questionnaire, forced vital capacity (FVC) testing and resting 3-lead ECG. The likelihood of obstructive sleep apnea will be evaluated using the STOP-BANG questionnaire. Subjects will be informed of their STOP-BANG questionnaire results, and if sleep apnea is suspected, then they will be referred for possible clinical treatment (which is outside of the scope of this study). If they choose to pursue clinical treatment for sleep apnea, then they will be included in the study after 3 months of treatment have elapsed. If they choose not to seek treatment, they will be included in the study. This plan is consistent with recommendations of a recent Intermittent Hypoxia workshop considering the inclusion/exclusion of subjects with sleep apnea; recommendations were made in based on input from two nationally known sleep apnea experts participating in that workshop (Drs. [name], University of Chicago, and [name] at Wayne State University).

At the screening session, subjects who meet all study criteria will be invited to participate in a third study session consisting of caffeine + AIH. Subjects who decline to participate in Aim 3 remain eligible to participate in Aims 1-2.

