#### **Screening Tests**

- Forced vital capacity the maximal volume of gas that can be forcefully exhaled, following full inspiration. FVC is a standard measure for clinical care and research, but lacks sensitivity in mild neuromuscular diseases, including ALS (58). Upright FVC will be conducted as per published American Thoracic Society and European Respiratory Society (ATS/ERS) guidelines (59-61). Study team will conduct FVC testing on screening/study visit #1 when any of the following conditions are present: (1) the most recent VC is <63% predicted, (2) most recent VC is >30 days from screening, or (3) written verification of the clinic VC is unavailable. Individuals with an FVC <60% of predicted will be ineligible for further participation in this study.

- 3-lead EKG cardiac rate and rhythm will be evaluated. The presence of resting tachycardia (HR>110 bpm), atrial fibrillation or other dysrhythmias will exclude

subjects from participation.

- Sleep apnea screening. Subjects
  - STOP-BANG questionnaire a validated screening tool for OSA (62). All subjects must complete the STOP-BANG questionnaire, which consists of 4 yes-no questions regarding the presence of symptoms of OSA, plus 4 questions regarding known physical risk factors for obstructive sleep apnea. Individuals who present with a high risk for OSA and are currently not receiving treatment (e.g. overnight positive pressure ventilation or mouthpiece) will be referred to a clinical sleep specialist for further evaluation.
  - Overnight sleep monitor subjects will have the option to wear an overnight sensor that non-invasively monitors arterial oximetry and actigraphy (WatchPAT, Itamar Medical), to estimate the severity of sleep-disordered breathing. Home-based peripheral arterial tonometry has a high specificity/sensitivity for detecting OSA (63). If clinically-significant OSA is detected by the sleep monitor (an apneahypopnea index >10 events/hour), subjects will be referred to a clinical sleep specialist for further evaluation.
  - Caffeine consumption questionnaire- subjects will be asked about their usual daily caffeine consumption habits. We will also ask the subjects about their possible reactions after consuming caffeine. This questionnaire will help us understand the responsiveness of the subjects to caffeine and help rule out individuals with adverse reactions to caffeine.

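### The systolic stopping criterion for AIH is purely relative (a change of more than 30% from rest), and the readable text sets no systolic limit for entry or for starting a session

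*Combined protocol and SAP*

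**What the plan says.** All references are to the combined protocol and SAP.

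- **Stopping criteria (Possible Discomforts and Risks).** AIH is stopped for a heart-rate change of more than 30% from rest in either direction, or if "systolic blood pressure changes more than 30% from the resting value". The participant may ask to stop at any time. SpO2 has a fixed floor: if it "falls below 75%, the AIH intervention will be terminated". The section adds that excessive heart-rate and pressure responses have not been reported.
- **Eligibility Criteria.** Participants "are between 21 and 75 years of age". They are ineligible if they "have diagnosed cardiovascular disease", a term the text does not define, or if the investigator or medical director considers another condition unsuitable. "Screening will include a detailed medical and pharmacological history, caffeine consumption questionnaire, forced vital capacity (FVC) testing and resting 3-lead ECG". When sleep apnea is suspected, treatment is offered by referral. "If they choose not to seek treatment, they will be included in the study".
- **Screening Tests.** Heart rate has an absolute entry limit: "The presence of resting tachycardia (HR>110 bpm), atrial fibrillation or other dysrhythmias will exclude" a subject. Neither section states a systolic value. The additional exclusions for the caffeine session do not mention blood pressure.
- **Caffeine + AIH.** The capsule follows baseline testing, and AIH begins one hour after it. The text does not say which reading is the resting value for the stopping rule.

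**The concern.** A percentage limit caps absolute pressure only if the starting value is itself capped. The other two physiological criteria have some fixed anchor: SpO2 has absolute floors, and resting heart rate has an entry limit. Systolic pressure has none in the readable text, so the pressure at which a stop becomes mandatory is highest for those who start highest.

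High resting pressure is foreseeable. Participants may be up to 75 years old, and people with suspected but untreated sleep apnea can enter. The exclusion for cardiovascular disease depends on a diagnosis, so it does not by itself catch undiagnosed high pressure.

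The caffeine session adds a smaller problem. If the resting value were taken after the capsule, any caffeine-related rise would lift the stop limit by 1.3 times that rise. What is at stake is participant safety, not an estimate.

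**Working it through.** The documents give no pressure figure to reproduce, so this is direct arithmetic on the stated rule.

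**Inputs from the documents:** the 30% systolic change; the 110 bpm entry limit; enrolment of up to 18 patients and 30 controls, for 12 and 20 completers. **Assumed:** resting pressures, candidate limits and pressure distributions.

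**1. Mandatory upper stop.** Stop limit = 1.30 × resting systolic.

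| Resting systolic, mmHg (assumed) | Stop required above, mmHg |
|---|---|
| 100 | 130 |
| 120 | 156 |
| 140 | 182 |
| 160 | 208 |
| 180 | 234 |

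From 160 mmHg, reaching 180 is a rise of 20/160 = 12.5%. A further 208 − 180 = 28 mmHg remains before the written rule requires a stop.

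**2. Comparison with heart rate.** 1.30 × 110 = 143 bpm is the highest upper stop, provided the session's resting rate stays within the screening limit. No such bound can be computed for systolic pressure.

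**3. Where an absolute ceiling C would act first.** C < 1.30 × rest, so rest > C/1.30.

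- C = 180: 180/1.30 = 138.5 mmHg.
- C = 200: 200/1.30 = 153.8 mmHg.

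Below those resting values the existing 30% rule still governs and nothing changes.

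**4. Effect of the proposed pair of limits** (start at or below 160, ceiling 180). The stop limit becomes the smaller of 1.30 × rest and 180: 156 from 120, 180 from 140, 180 from 160. Even at 160 the participant has 20 mmHg, or 12.5%, of room before a stop.

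**5. Participants lost to a 160 mmHg start limit.** The base is everyone enrolled, 18 + 30 = 48, because the limit acts before completion. Normal distributions are assumed.

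| Mean, SD (mmHg, assumed) | Share resting above 160 | Expected of 48 |
|---|---|---|
| 120, 12 | 0.04% | 0.02 |
| 125, 15 | 1.0% | 0.5 |
| 130, 15 | 2.3% | 1.1 |
| 135, 18 | 8.2% | 3.9 |

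The range is about 0 to 4. The enrolment allowance over planned completers is 48 − 32 = 16. These models make no adjustment for people already excluded by diagnosis or discretion, so the upper end is probably too high.

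**The case against.** The strongest reply is that the rule does not stand alone and no harm is documented. Heart rate, SpO2 and participant request also stop AIH, subjects are monitored throughout, and the data safety monitoring board meets after the first three patients and can be convened by an event. A detailed history may reveal known hypertension, which the cardiovascular exclusion or clinical discretion may then keep out. All of this stands and narrows the gap to undiagnosed or uncontrolled pressure. None of it supplies a pressure at which AIH must not start or must stop.

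Several stronger readings are tempting but unsupported:

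- *AIH stops only on systolic pressure.* It does not. Relative-only describes the pressure criterion, not the whole set of stops.
- *A participant resting at 160 would be kept on AIH up to 208.* The section says when a stop is mandatory. It does not tell staff to continue below that point.
- *The protocol's own background shows that this AIH raises pressure.* The Background says that high doses simulating sleep apnea "elicit pathology, including systemic hypertension, neuroinflammation, and cognitive impairment", but contrasts them with low-dose AIH. Possible Discomforts and Risks associates milder protocols with reduced blood pressure. It also says that similar AIH protocols increase sympathetic nerve activity, so the text does not settle the matter either way.
- *Caffeine at the study dose raises pressure.* The plan attributes possible rises to higher doses and describes neutral or protective cardiovascular effects. Fixing the resting value before the capsule is a precaution.
- *Blood pressure is not measured at screening.* Figure 1, which covers the screening procedures, is not shown and may include a reading. The point is confined to the absence of a limit in the readable criteria.

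**Conclusion.** The point holds as a gap in a written safety rule. The systolic criterion is purely relative, its starting value is unbounded in the readable text, and the mandatory stop is therefore 1.3 times whatever the resting value is: 182 mmHg from 140 and 208 mmHg from 160.

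The arithmetic is certain. How often it would matter is not. The resting values are illustrative, the documents contain no pressure data, and the number of participants who would approach any ceiling cannot be estimated from them. The plan reports that excessive responses have not been seen. The change is worth making because it is cheap and closes the gap where the existing rule is loosest, not because harm has been shown.

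**What to change.** In Possible Discomforts and Risks:

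1. Stop AIH at a 30% systolic change or at a stated absolute ceiling, whichever is reached first. A value such as 180 mmHg is an example for the study's clinicians to set.
2. Do not start a session if seated resting systolic pressure is above a stated limit, for example 160 mmHg. Apply this to AIH, Sham AIH and caffeine sessions alike, so that the conditions share the same entry rule.
3. Define the resting value as the seated reading before episode 1. In the caffeine session use the reading before the capsule, so that any caffeine-related rise counts towards the limit.

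The cost is a few sentences. The existing rule already needs a resting and an in-session systolic reading, so the ceiling adds no measurement. In the caffeine session the resting reading moves to before the capsule, and Sham AIH needs a resting reading if none is taken now. The downside is that about 0 to 4 of up to 48 enrolled may be excluded under the assumed distributions, and some sessions may be stopped early. The number stopped early cannot be estimated from the documents.
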